10.2.4 Definition of analysis population related to protocol non-adherence

As described above, intention to treat analyses will be conducted on the primary and secondary outcomes. All neonates will be included, regardless of protocol adherence, to prevent the effects of attrition bias.

We will also report results of per protocol analyses and complier average causal effects to account for children for whom major protocol violations were recorded such as those relating to non-compliance with the study treatments.

10.3 Analysis Plan for Economic Data

To model DALYs and costs over a lifetime time horizon in accordance with reference case specifications, we will firstly calculate the costs and discounted years of life lost (YLLs) due to neonatal deaths within the neonatal period measured in the trial. Secondly, for neonates who survive beyond 1 month, we will develop a Markov model to estimate the costs and discounted years of life with disability (YLDs) lost and additional YLLs from premature mortality attributable to health conditions associated with prematurity and LBW. If there is a difference between trial arms in rates of breastfeeding, the impact on morbidity and mortality of the differential rates of breastfeeding will also be modelled. The model structure and parameters will be informed by existing literature (47) and by consultation with clinical experts, including the PI and other members of the trial team. If neither intervention exhibits strict dominance (i.e., is less costly and more effective), we will model incremental cost per neonatal death averted and per DALY averted, in line with reference case specifications. Deterministic and probabilistic sensitivity analyses will be conducted to assess the robustness of results to uncertainty and heterogeneity.

We will examine budget impact by using the incremental financial costs incurred in the trial context to project how these costs may vary at scale and which budgets would bear the incremental costs or reap the cost savings. For example, we envisage additional cost burden at the national level to train on KMC, which is likely to require donor support, but potential cost savings at the hospital level in reduced equipment and maintenance costs. We will compare cost burden with existing budgets, where relevant, and engage with policy makers to understand affordability at different levels.

Equity will be explored by examining variation in incremental costs to households and in health and well-being outcomes across socioeconomic groups.

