KMC works through multiple pathways, many of which are mediated by skin-to-skin contact triggering a primary neuro-endocrine mechanism involving oxytocin as a key mediator with systemic effects in both mother and neonate. The key causal pathways underpinning the protective benefit of KMC are: thermal control; reduction in cortisol and stress response; cardio-respiratory stabilisation; enhanced breastmilk supply and breastmilk feeding; and empowering the mother as key carer for her baby. Although previously extensively researched in stable babies receiving skin-to-skin contact, the validity and relative contribution of these pathways in skin-to-skin contact in neonates prior to stability is not fully known. Further research is therefore warranted to improve our understanding of the physiological processes underpinning any potential benefit of KMC in this population.

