6.3.1 Understanding causal pathways for clinical effects

Understanding the causal pathways for clinical effects of the intervention (Objective 2) will be achieved by measurement of the following process outcomes, which are categorised as providing very early (within 24 hours), early (within 72 hours), or late clinical impact:

Very early impact:

- Cardio-respiratory stability within 24 hours post-randomisation
- Prevalence of hypothermia within 24 hours post-randomisation
- Hypothermia density within the first 24 hours post-randomisation
- Prevalence of hypoglycaemia within 24 hours post-randomisation

Early impact:

- Cardio-respiratory stability within 72 hours post-randomisation
- Prevalence of hypothermia within 72 hours post-randomisation
- Hypothermia density within the first 72 hours post-randomisation
- Prevalence of hypoglycaemia within 72 hours post-randomisation
- Presence and severity of IVH within 72 hours post-randomisation

Late impact:

- Presence and severity of IVH at day 7
- Proportion of neonates exclusively breastmilk feeding at discharge
- Presence of late intracerebral sequelae of prematurity (e.g., hydrocephalus, cystic degeneration) at day 28-30

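### The lifetime economic model includes the post-neonatal breastfeeding pathway only if the trial shows an undefined difference between arms; it should always be included, with its uncertainty

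*Protocol*

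**What the plan says.** Section 10.3 builds the lifetime model in two steps. Costs and years of life lost from deaths in the neonatal period are taken directly from the trial. A Markov model then carries survivors beyond one month.

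The breastfeeding component is conditional: "If there is a difference between trial arms in rates of breastfeeding, the impact on morbidity and mortality of the differential rates of breastfeeding will" enter that model. No test, threshold, measure or time point is given for the condition.

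Other text that bears on it:

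- Section 10.3, on inputs: "The model structure and parameters will be informed by existing literature", together with expert consultation.
- Section 10.3, on uncertainty: "Deterministic and probabilistic sensitivity analyses will be conducted to assess the robustness of results to uncertainty and heterogeneity". It does not say whether the breastfeeding effect remains in these analyses when no difference is declared.
- Section 2.1 lists "enhanced breastmilk supply and breastmilk feeding" among the key causal pathways of KMC, and adds that the contribution of these pathways before stability is not fully known.
- Two collected measures could serve as the trigger: "Proportion of neonates exclusively breastmilk feeding at discharge" (a process outcome, section 6.3.1) and breastfeeding status at the day 28-30 visit (section 6.1.5). The related secondary outcome in section 1.4.2 is a time to exclusive breastmilk feeding, not a rate.
- Section 10.2.2 sets P<0.05 for the primary and secondary outcome analyses. Nothing ties it to the condition in section 10.3.

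**The concern.** Whether a pathway belongs in a decision model should follow from what is believed about the mechanism. Its size and uncertainty should come from the data. Here the data also decide whether the pathway exists in the model, although the protocol itself names breastmilk feeding as a mechanism of KMC.

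If the condition is applied as a significance test, it acts as a pre-test on the parameter. A modest real effect is often left out and, when it does enter, has been selected for being large. When the pathway is left out, so is the uncertainty about it, although failing to detect a difference does not show that the effect is zero.

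At stake is secondary objective 2, the cost-effectiveness of KMC. Because the trigger is undefined and at least two measures could supply it, the choice could also be made after the results are known.

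**Working it through.** **Plan's own figure.** The protocol gives no figure for the breastfeeding condition. The survivor numbers below rest on the sample size in section 10.1, so that is checked first. For 25% versus 19.4% (25 − 5.6), two-sided 5%, 80% power:

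n per arm = [1.96·√(2·0.222·0.778) + 0.842·√(0.25·0.75 + 0.194·0.806)]² / 0.056² = 864

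The protocol states 875, at which power is 80.5%. Inflation: 1750/0.80 = 2187.5, hence 2188. Both figures reproduce.

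**Inputs for the illustration**

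- From section 10.1: 1094 recruited per arm and 25% control mortality.
- Assumed: 75% of controls and 80% of KMC infants survive to be measured (the 19.4% above would imply 80.6%), giving 1094 × 0.75 ≈ 820 and 1094 × 0.80 ≈ 875.
- Assumed: the condition is a two-sided 5% test; control breastfeeding p0 is 50-90%; the true gain d is 2 to 8 points.

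**Formulas**

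- SE = √[p0(1−p0)/n0 + p1(1−p1)/n1], with p1 = p0 + d
- a = 1.96 − d/SE and b = −1.96 − d/SE
- P(enters) = [1 − Φ(a)] + Φ(b)
- Mean when entered = d + SE·[φ(a) − φ(b)] / P(enters)

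**Worked case: p0 = 70%, d = 3 points**

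- SE = √(0.70·0.30/820 + 0.73·0.27/875) = 0.0219
- a = 1.96 − 1.367 = 0.593; b = −3.327
- P(enters) = 0.277
- Mean when entered = 0.0564, that is 5.6 points, or 1.88 times the truth
- Mean over all trials, counting an omitted pathway as zero: 0.277 × 5.64 = 1.6 points against a true 3

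**Range over control rates of 50-90% (820 and 875 survivors)**

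| True gain | Pathway enters | Overstatement when it enters |
|---|---|---|
| 2 points | 13-30% | 1.8-2.9 times |
| 3 points | 24-60% | 1.3-2.1 times |
| 5 points | 54-97% | 1.02-1.4 times |
| 8 points | 91-100% | 1.00-1.05 times |

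A true zero enters as a false difference 5% of the time.

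With the 1750 analysed in section 10.1 instead (656 and 700 survivors), a 3-point gain enters 20-51% of the time, overstated 1.4-2.25 times. An 8-point gain enters 84-100% of the time, overstated by at most 10%.

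**Other reading.** If any non-zero observed difference meets the condition, it is almost always met and adds essentially no bias.

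**Always included.** The estimated difference enters every time, so there is no selection and the expected overstatement factor is 1.00. Its standard error (2.2 points in the worked case) passes into the probabilistic analysis.

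**The case against.** The strongest reply is that the significance test is not in the protocol. Section 10.3 names none, and the P<0.05 criterion belongs to section 10.2.2. Read plainly, the sentence may mean only that whatever differential is seen will be carried forward. That stands, and under that reading there is no material harm. But the condition then does no work, and deleting it loses nothing.

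A second reply is that section 2.1 regards the pathways as not established before stability, so conditional inclusion is a reasonable structural choice. The caveat is fair. It argues for entering the effect with wide uncertainty, not for switching it on or off according to one comparison.

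A third reply is that measure, time point and distributions belong in a later analysis plan, and that sensitivity analyses are already promised. Leaving those details to a later plan is no fault. The conditional rule itself, however, is fixed in the protocol, and the promise of sensitivity analyses does not say whether an omitted pathway is covered.

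Two stronger readings are tempting and are not supported:

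- A reader might infer that the condition must either erase a real effect or inflate it. This holds only for modest effects under a test; at 8 points the distortion is small.
- A reader might see the dominance clause ("If neither intervention exhibits strict dominance (i.e., is less costly and more effective), we will model incremental cost per neonatal death averted") as a second fault of the same kind. It is not. Withholding a ratio when one option is both cheaper and more effective is conventional, and incremental costs and effects are promised elsewhere without condition (sections 1.3 and 3.3).

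**Conclusion.** The point holds as a minor one. Section 10.3 makes the structure of the lifetime model depend on an undefined trial result, and a better method is available at almost no cost.

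The size depends on the reading. Under an assumed two-sided 5% test with 820 and 875 survivors and control breastfeeding of 50-90%, a true 3-point gain is left out of 40-76% of trials and overstated 1.3-2.1 times otherwise. For an 8-point gain the overstatement is about 5% or less. If any non-zero estimate counts, the effect is negligible.

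A reader might infer that the whole cost-per-DALY result turns on this switch, or that its interval is shown to be too narrow. The protocol supports neither. Deaths in the neonatal period are counted from trial data without condition, so only the post-neonatal addition is affected. The protocol gives no breastfeeding rates and no link from breastfeeding to later morbidity or mortality, so the effect on cost per DALY cannot be computed. What can be said is that, when the condition is not met, this source of uncertainty is left out. The primary and secondary clinical analyses are untouched.

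**What to change.** In section 10.3, or in the health-economics plan that implements it:

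1. Delete the condition and always include the post-neonatal breastfeeding pathway.
2. Name in advance one measure already collected, for example exclusive breastmilk feeding at discharge or breastfeeding status at day 28-30.
3. Enter the estimated between-arm difference on that measure, with its standard error, as a distribution in the planned probabilistic sensitivity analysis.
4. Show one scenario without the pathway, so that readers can see what it contributes.

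The cost is a wording change, one more parameter in a model already planned, and slightly wider uncertainty around cost per DALY. No new data are needed and trial conduct does not change.

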10.4 Analysis Plan for Qualitative Data

Interview/FGD data will be transcribed and, where necessary, translated into English. Data will be analysed using the thematic content approach (70,71). Using this approach, data analysis will consist of four steps: (1) familiarisation; (2) identifying codes and themes; (3) developing a coding scheme and applying it to all of the data; (4) organising codes and themes. [name] and the Ugandan interviewer will read all interview/FGD transcripts and develop the preliminary coding schemes together. [name] and the interviewer will individually code 10% of transcripts from each portion of the qualitative evaluation. Any discrepancies will be discussed and resolved to develop the final coding frameworks. [name] will code all remaining transcripts. New themes that emerge outside the

coding framework will also be included in the analysis (72,73). Qualitative manuscripts will follow the consolidated criteria for reporting qualitative research (74).

11. Quality Control and Quality Assurance

The PI will ensure that staff involved with the trial are:

- Properly qualified to assume responsibility for conduct of the study
- Willing to comply with GCP and applicable regulations
- Prepared for audits and monitoring
- Able to recruit study participants in sufficient numbers and on time
- Well informed about the protocol and their study responsibilities The site clinical leads will ensure that their respective sites have:
 - Sufficient human and material resources to sustain routine standards of care
 - Staff who are well informed about the protocol, the IP, and their study responsibilities and are fully trained in the relevant SOPs

11.1 External Monitoring

The study will be monitored by the Clinical Studies Support Office at MRC/UVRI, who will develop a risk-based monitoring plan for the study. The monitoring team comprises of trial coordinators and trial managers from the various trials currently running within the unit. To achieve independence during the monitoring, one dedicated study monitor, independent of the study team, will be assigned to monitor this study. The monitor's role is part of the quality system and will oversee the progress of the trial and ensure that the trial is conducted and data are handled in accordance with trial SOPs, the protocol, Good Clinical Practice (GCP) and applicable ethical and regulatory requirements.

11.2 Internal Monitoring

Internal monitoring will be conducted by the central study team (PIs and trial coordinator) as a continuous process through direct communication with the site paediatricians and medical research officers via telephone or email and physical site visits.

11.3 Audits and Inspections

The study may be subject audit by the London School of Hygiene & Tropical Medicine under their remit as sponsor, the Study Coordination Centre and other regulatory bodies to ensure adherence to GCP.

11.4 Indemnity

London School of Hygiene & Tropical Medicine holds Public Liability ("negligent harm") and Clinical Trial ("non-negligent harm") insurance policies that apply to this trial.

12. Data Management

At the hospitals, trial data will be electronically entered on tablets into a GCP-compliant, offline, trialspecific mobile application [Research Electronic Data Capture (RedCap), Nashville, TN, USA]. REDCap has a built-in audit trail that automatically logs activity including log-ins, user rights, data entry/modification, data export, and running reports. Only the PIs, the trial coordinator, and the data managers will have access to this database.

12.1 Data Transmission and Editing

Data from tablets, which will be partially anonymised (participant names excluded), will be synced once daily over a secure 3G connection with a web-based RedCap database. The system will be centrally hosted at the MRC/UVRI data centre. Anonymised pulse oximeter and temperature logger recordings (linked by participant ID) will be captured in MS Excel files, securely transmitted to MRC/UVRI, and entered into the trial database. Data including pulse oximeter / temperature recordings, will be transferred to Stata for analysis. Cranial ultrasound images will be stored in OsiriX Dicom imaging software and interpreted blind to allocation and clinical details. Logs linking parent/guardian names and residence location will be stored separately on a password-protected computer, with a hard copy stored in locked cabinets in secure rooms at the sites.

We will utilize the inbuilt access management and audit trail functions of REDCap to track changes to the data, implement role assignment and restrict unauthorized access to study data.

12.2 Data Discrepancy Inquiries

REDCap has a built-in audit trail that automatically logs activity, including log-ins, user rights, data entry/modification, data export, and running reports. Only the PIs, the trial coordinator, and the data managers will have access to this database.

Internally developed Stata verification/cleaning do-files will be run by data managers to identify data that are missing, inconsistent, or out-of-range. The trial coordinator will perform clinical quality checks to identify potential errors not captured in the automated verification process.

Query resolution: The trial coordinator or data managers will raise queries through the RedCap query management system and assign it to a member of the study team at the respective site, who will respond to it. Only after a satisfactory response is given will the query be closed. Pending queries will be allowed up to 2 days if the patient is still hospitalised or 5 days if patient has been discharged.

12.3 Qualitative Data

To ensure a standardized approach is used for FGDs/interviews at all sites, interviewers will be issued a FGD or interview guide and a pre-specified list of target respondents. FGD/interview data will be collected, with consent of participants, through audio-recording and field notes. Transcripts will be linked by study ID to other forms of data collected for the study. Master records with ID numbers and identifying information will be stored separately.

12.4 Security and Backup of Data

All data will be stored in institutional servers at MRC/UVRI during the study. A complete backup of the database onto external hard drives will be performed twice per month. Hard drives will be stored at MRC/UVRI and retained for a minimum of three years after publication of the research. Audio files will be digitally recorded and securely stored on a computer as password protected files until transcription and verification are completed. At the end of the study, all study documents with names or addresses will be destroyed.

Data from the web-based RedCap database will be downloaded and stored on institutional servers at LSHTM for access by the PIs and independent statistician for analysis and preparation of reports for the DSMB, respectively. These secure, password-protected servers are only accessible within the LSHTM network from specified user accounts. Access is controlled by Firewall policy based on the host address

and application. Activity on LSHTM servers are fully audited recording both login details and file system access. Access will be limited to essential research personnel.

No names or other direct identifiers will appear in typed documents, transcripts, or recordings. FGD/IDI transcripts will be pseudo-anonymised with unique confidential codes and identification codes will be kept in a separate secure location. The electronic master-log linking participant-identifying information will be stored on a password-protected computer and a hard copy master-log stored in a locked filing cabinet under the custody of the trial coordinator. Consent forms will be stored in locked cabinets in secure rooms at the sites.

12.5 Study Status Reports

The data manager at MRC/UVRI will prepare weekly email reports with information on missing and incongruent data. The trial coordinator will review these reports and inform the data manager regarding any necessary corrections.

12.6 Access to Data

Data from the web-based RedCap database will be downloaded and stored on institutional servers at LSHTM for access by the PIs and independent statistician for analysis and preparation of reports for the DSMB, respectively. These secure, password-protected servers are only accessible within the LSHTM network from specified user accounts. Access is controlled by Firewall policy based on the host address and application. Activity on LSHTM servers is fully audited recording both login details and file system access. Access will be limited to essential research personnel.

12.7 Responsibilities

The PIs, trial coordinator, data advisor, and data managers will be responsible for data management, quality assurance, and data security. [name] (UK data manager) will be responsible for metadata creation and data sharing. Policies of the LSHTM Research and Governance Office will govern study-wide data management and metadata creation activities, and policies of LSHTM Information Technology will govern data security.

13. End of Trial and Archiving

At the termination of planned recruitment, the Trial Coordinating Centre will contact the site by telephone or email in order to terminate all patient recruitment as quickly as possible. If the study is terminated prematurely by the Steering Committee, the site will be informed immediately. When all recruited patients have been followed until hospital discharge or death, a declaration of the end of trial form will be sent to the relevant IRBs. The following documents: original consent forms, data forms, trial related documents and correspondence, will be archived in the Site File and kept for at least five years. At the end of the analysis and reporting phase, the Trial Master Files at the Trial Coordinating Centre will be archived for 15 years.

14. Ethical Considerations

14.1 Ethical approvals and general considerations on human subject participation

Approval will be obtained from the UVRI Research Ethics Committee, the Uganda National Council for Science and Technology, and LSHTM. Annual progress reports will be submitted to the IRBs within 30

days of the anniversary date on which the favourable opinion was given until the trial is declared ended. The PI will notify the IRBs of the end of the study. Substantial amendments that require review by IRB will not be implemented until the IRB grants a favourable opinion for the study. All correspondence with the IRB will be retained in the Investigator Site File.

14.2 Rationale for inclusion of vulnerable groups

14.2.1 Rationale for Neonates

Our study aims to investigate KMC, initiated before stabilisation, amongst neonates $\leq 2000\text{g}$. As such, we are obligated to study neonates. These small neonates are at high risk, and in these low-resource Ugandan hospitals without intensive care, standard care using incubators, often shared with other neonates, exposes them to significant risks (e.g., infection). KMC has been shown to reduce many of these risks and could have major mortality gain. WHO and others have stated that determining the effect of KMC initiated prior to stabilisation is an important and justifiable research question, notwithstanding these risks. Our team includes neonatal trialists, including an expert in ethical issues in neonatal trials, and we will address concerns through careful monitoring of neonates and DSMB monitoring.

14.2.2 Rationale for children ≥ 15 years of age (who are parents of included neonates)

According to the Uganda National Council of Science and Technology, “emancipated minors are individuals below the age of majority who are pregnant, married, have a child or cater for their own livelihood,” and “mature and emancipated minors may independently provide informed consent to participate in research” (75). Uganda has a high rate of teenage pregnancy. According to the Uganda Demographic Health Survey (UDHS 2011), 24% of women are already mothers or pregnant with their first child before the age of 19, and 39% of women aged 20 to 49 gave birth by age 18 (2).

